4.4. Aerobic exercise in clinical practice

UK stroke rehabilitation guidelines recommend that walking-orientated activities should have a cardiorespiratory focus (49). In clinical practice, walking is undertaken at low intensities for very short periods of time. For example, Prajapati et al., (50) reported that in subacute stroke patients (mean 32 days post-stroke), over 80% of walking bouts were less than 1 minute long and mean walking intensity was 20% of HRR. Polese et al., (51) reported similar findings in chronic stroke survivors (mean 26 months post-stroke), where basic and advanced walking activities elicited intensities of 26% and 32% of HRR, respectively. The only study which has reported inpatient walking activity during the acute phase of stroke

found that elderly patients spend less than 1 minute per day walking (52) and time spent inactive was positively correlated with stroke severity (HR not reported). During the first week of stroke ~70% of patients have a lower limb motor deficit (53) and ~60% are unable to walk or require walking assistance (54,55). A more accessible and tolerable mode of aerobic exercise may therefore be necessary to achieve a cardiorespiratory stimulus of sufficient intensity (moderate) and duration (20 to 30 minutes) to elicit elevations in CBF and mBDNF.

4.5. Accessibility of aerobic exercise

Findings from patient and practitioner surveys (56,57) and our PPI events highlight that physical disability, lack of appropriate exercise equipment and fear of falling are key barriers to engagement in aerobic exercise during acute stroke. These barriers may exclude patients who have the most to gain from participating in aerobic exercise training. We will utilise a bedside cycle ergometer with a power assistance function (Figure 2; Letto 2, Medimotion, Germany). This will enable participants to cycle even if they have hemiplegia or hemiparesis, without needing to be transferred out of their bed. Using a bedside cycle ergometer eliminates the risk of falling and enables people with lower limb motor deficits to participate in sustained aerobic exercise. Another benefit of using a bedside cycle ergometer is that participants exercise in a semi-recumbent position. In contrast to walking which may induce orthostatic stress (47), moderate-intensity semi-recumbent cycling is likely to preserve or increase cerebral perfusion (30). Our preliminary (ongoing) work supports this hypothesis; we have shown that in acute stroke patients (n=4), a single 30-minute bout of low- to moderate-intensity aerobic exercise is safe and tolerable, and increases CBF velocity by 9% above resting levels. We will build on this work by assessing the feasibility of an aerobic exercise training intervention versus standard care in the acute phase of stroke.

Figure 2. A bed-side power-assisted cycle ergometer (Medimotion, Letto 2).

5. Aims and objectives

Aim 1: To assess the feasibility of conducting a RCT to assess the intervention.

Objectives:

- 1a) Assess the recruitment/consent and dropout rates
- 1b) Assess the safety of the intervention via SAEs and AEs
- 1c) Assess the completeness of planned data collection

Aim 2: To assess the acceptability and feasibility of the intervention.

Objectives:

- 2a) Determine the retrospective acceptability of the intervention from the participant perspective using qualitative interviews and Likert scales.
- 2b) Determine the retrospective acceptability of the intervention from the perspective of healthcare practitioners using qualitative interviews.
- 2c) Determine the intervention fidelity by assessing the extent to which participants complete the prescribed exercise components (e.g. exercise intensity, duration and frequency).

Aim 3: To develop mechanistic knowledge of the intervention.

Objective:

- 3a) Measure the acute physiological response to the intervention including CBF velocity and mBDNF.

Aim 4: To identify potential primary outcomes for a subsequent definitive RCT.

Objective:

- 4a) Estimate the effect signal for potential primary outcome measures. The effect signal reflects the effectiveness of the intervention (difference between means of the groups) and the 'noise' (inter-individual variability) in the measurement (i.e. precision of the measure) and will inform the selection of primary outcome for a subsequent definitive RCT.

6. Study overview

6.1. Study design

A phase II, single-centre, single-blinded, two-arm, parallel group, randomised, controlled feasibility trial.

6.2. Study setting

The study will be conducted at The Royal Hallamshire Hospital (RHH), Beech Hill Rehabilitation Unit (BHRU) and the Advanced Wellbeing Research Centre (AWRC), Sheffield. Most study activity (screening and intervention) will take place on the hyper acute stroke unit (HASU), the acute stroke unit (ASU) or the neurology day care unit at RHH. Follow-up visits will be conducted at either the RHH, BHRU or the AWRC.

6.3. Success criteria

Progression to a definitive trial will be considered if the following a priori success criteria are met:

- Recruitment rate: ≥ 2 participants per month (30 participants recruited in 18 months)
- Safety - The following traffic light-style system is proposed:
 - Red: >10 adverse events related to the intervention – do not proceed.
 - Amber: 5-10 adverse events related to the intervention – review and revise protocol.
 - Green: <5 adverse events related to the intervention – proceed.
- Acceptability: average comfort score $> 3/5$ Likert scale (1= very uncomfortable to 5= very comfortable).
- Completeness of data: $>80\%$ of planned measurements recorded.
- Identification of an appropriate outcome measure.

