Trial participants	Acute ischaemic stroke patients (1-7 days post stroke)	
Planned sample size	30	
Intervention duration	5 working days	
Trial duration per participant	3 months	
Estimated total trial duration	21 months	
	Objectives	Outcome Measures
Primary	To determine the feasibility of conducting a randomised controlled trial (RCT) to assess the effects of an aerobic exercise intervention on stroke outcomes.	
 • safety • recruitment rate • exclusion rate • consent rate • dropout rate • participant fidelity to intervention • acceptability • completeness of data
Secondary	To identify potential primary outcomes for a subsequent definitive RCT.	
For example:
 
 • physical function/disability • health-related quality of life • cognitive function • mood • fatigue

	To develop mechanistic knowledge of the intervention.	
 physical activity levels Cerebral blood flow velocity Mature brain-derived neurotrophic factor
Type of intervention	Power-assisted aerobic exercise training.	
Intervention components	A 10-30 minute session of low-moderate aerobic interval exercise conducted once per day for 5 working days. Exercise type: semi-recumbent power-assisted in-bed cycling.	

iii. Funding and support in kind

Funder(s)	Financial and non-financial support given

Sheffield Hallam University
 
[contact]
 
Email: [contact]
	
Vice Chancellor's PhD Scholarship:
 
£15,009 per annum salary for PhD student for 3 years (£45,027)
 
£1,500 per academic year for research-related costs including consumables, patient transport and research dissemination (£4,500)
 
Total = £49527

Sheffield Teaching Hospitals NHS Foundation Trust, Department of Neurosciences.
 
[contact]
 
Email: [contact]
	
Transcranial Doppler ultrasound device provided in kind.
 
Cycle ergometer provided in kind.

iv. Role of Sponsor and Funder

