7.1. Patient throughput and planned recruitment

According to NHS England figures, RHH HASU will receive approximately n=1335 stroke patient admissions in 2019/20 (58). 85% of these patients will have had an ischaemic stroke (6), thus, ~1135 ischaemic stroke survivors will potentially be eligible for our study per year (n=1700 in 18 months). A systematic review of recruitment rates in stroke rehabilitation trials suggests that 1.5 to 2 participants per month is a realistic target for a single site (59); hence, our recruitment target of 30 patients over 18 months.

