7.3. Sample size

A minimum of 24 participants (12 per arm) will be recruited. 12 has been recommended as a minimum number of participants per arm to be recruited for a clinical trial where there is no prior information to guide sample size (60). This figure is suggested to represent the lower threshold required to estimate the standard deviation of measures with adequate precision (60). Adjusting for a predicted 20% attrition rate, the target sample size is 30.

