Recruitment rate	Number of participants recruited per month of the recruitment period.
Exclusion rate	Number of ineligible patients divided by the total number of patients admitted to the RHH stroke service during the recruitment period.
Consent rate	Percentage of eligible patients who consent to participate.
Dropout rate	Percentage of individuals that discontinue participation after the study has commenced. Voluntary reasons for dropout will be recorded. Early discharge from hospital will not count as a dropout.
Participant fidelity	Completion of key exercise components in accordance with the exercise protocol including: percentage of planned exercise session duration completed, percentage of target exercise intensity per session attained, and percentage of total planned exercise sessions completed.
Completeness of data	Percentage of planned measurements completed and recorded.
Safety	Number of SAE and AEs related to the intervention.
Acceptability of intervention (participant interview)	Comfort and ease of using cycling apparatus.
Acceptability of study procedures (healthcare professional interview)	
 • Attitudes towards the intervention • Burden on staff and participants • Perceived effectiveness of the intervention

12. Intervention

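### The recruitment criterion contradicts itself: 30 participants in 18 months is 1.67 per month, so recruiting exactly to plan fails the stated minimum of 2 per month

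*Protocol*

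**What the plan says.** Section 6.3 introduces the list with "Progression to a definitive trial will be considered if the following a priori success criteria are met". The first item is "Recruitment rate: ≥ 2 participants per month (30 participants recruited in 18 months"). The bracket reads as a restatement of the rate, and nothing says which of the two governs if they differ.

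The other relevant places are:

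- Section 11, Table 6, defines recruitment rate as "Number of participants recruited per month of the recruitment period".
- Section 7.1 derives the plan from a review of stroke rehabilitation trials: "1.5 to 2 participants per month is a realistic target for a single site (59); hence, our recruitment target of 30 patients over 18 months".
- Section 7.3 fixes the number: "Adjusting for a predicted 20% attrition rate, the target sample size is 30".
- The trial summary lists recruitment rate among the primary outcome measures. It also gives 3 months per participant and 21 months for the "Estimated total trial duration".

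**The concern.** A threshold written with a greater-than-or-equal sign is a decision boundary. Here the boundary is given twice, with two different values. Judged by the bracket, a trial that delivers its own recruitment plan has succeeded; judged by the rate in front of the bracket, it has failed.

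Recruitment rate is a primary feasibility outcome and one of five criteria for considering a definitive trial. If the data fall between the two boundaries, whoever writes the report must choose which half to apply, knowing the result. Setting the criteria a priori was meant to prevent that.

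**Working it through.** **Inputs.** Target 30 participants (Sections 6.3, 7.1, 7.3 and trial summary). Recruitment period 18 months (Sections 6.3 and 7.1). Stated minimum rate 2 per month (Section 6.3). Planning range 1.5 to 2 per month (Section 7.1). Minimum sample 24 with 20% attrition (Section 7.3). Total duration 21 months and 3 months per participant (trial summary).

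**Step 1: the target and the period reproduce.**
- Target: 24 / (1 − 0.20) = 30, as stated.
- Period: 21 − 3 = 18 months, which agrees with Section 7.1.
- Planning range: 1.5 × 18 = 27 and 2 × 18 = 36, so 30 lies inside it.

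**Step 2: the rate does not reproduce.** By the Table 6 definition, rate = participants / months of recruitment:
- 30 / 18 = 1.67 per month, below 2.
- 2 / 1.667 = 1.20, so the stated minimum is 20% above the planned rate.
- At 2 per month, 30 participants take 30 / 2 = 15 months, and 18 months yield 2 × 18 = 36 participants.

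**Step 3: look for a denominator or count that rescues the 2.**
- The full trial duration gives 30 / 21 = 1.43 per month.
- The minimum sample gives 24 / 18 = 1.33 per month.
- Only rounding 1.67 to a whole number gives 2. The protocol states no rounding rule, and 1.67 does not satisfy a minimum of 2.

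**Step 4: where the verdicts conflict.** With 30 as the target, recruitment ends at the 30th participant:

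| 30th participant enters | At least 2 per month | 30 in 18 months |
|---|---|---|
| By month 15 | met | met |
| After month 15, by month 18 | not met | met |
| After month 18 | not met | not met |

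Finishing exactly on plan, at month 18, falls in the middle row.

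**Step 5: how likely is the middle row?** The protocol gives no accrual model. As an illustration, assume that the number recruited by month t, N(t), is Poisson with mean rate × t. The chance of conflict is then P(N(18) ≥ 30) − P(N(15) ≥ 30).

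| True rate per month | P(30 by month 15) | P(30 by month 18) | Chance of conflict |
|---|---|---|---|
| 1.5 | 0.075 | 0.307 | 0.232 |
| 30/18 = 1.67 | 0.182 | 0.524 | 0.342 |
| 2.0 | 0.524 | 0.862 | 0.338 |

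At the planned rate, the literal minimum of 2 per month would be reached about 18% of the time.

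**The case against.** The best counter-argument is that the intended meaning is plain and the consequence modest. Everything else in the protocol points to 30 in 18 months, and the 2 is most likely 1.67 rounded to whole people. Progression is only to be considered when the criteria are met, so nothing stops automatically. Recruitment is one of five criteria, and the slip touches no participant's treatment, the randomisation, the data collected or any effect estimate. Count, dates and rate can all be reported whichever half is used.

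Much of this is fair. It shows which half to keep, and it limits the harm to the progression decision. It does not remove the contradiction: no place in the protocol says that the bracket governs, and a minimum cannot be met by a lower figure that rounds to it.

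Three narrower points also stand:

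- The conflict should be described by when the 30th participant enters, and not by any observed rate between 1.67 and 2. Closing early at 27 in 16 months (27/16 = 1.69 per month) fails both halves. Stopping at 29 in 14 months (29/14 = 2.07) passes the rate and fails the count.
- The Poisson probabilities illustrate the size of the problem and do not establish it.
- The split of 21 months into 18 + 3 is an inference; the protocol gives the total without a breakdown. The 18-month period does not depend on it, since Sections 6.3 and 7.1 state it directly.

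**Conclusion.** The criterion is wrong as written. Under the protocol's own definition, 30 participants in 18 months is 1.67 per month, so the planned result cannot satisfy a minimum of 2 per month. The gap is 20% in rate, or three months in time to 30 participants (15 against 18). This conclusion needs only the figures in Sections 6.3, 7.1 and 11.

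The chance of a conflicting verdict, about 23% to 34% at the three rates examined, rests on the added assumption of Poisson accrual at a constant rate and of recruitment ending at 30. The error is confined to the rate in Section 6.3; the sample size and the recruitment period are consistent. Because it concerns a decision threshold on a primary feasibility outcome, it should be corrected before results are known.

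**What to change.** Replace the recruitment item in Section 6.3 with a single test that matches the plan: *30 participants recruited within 18 months (about 1.7 per month)*. Make the count and the period binding and delete the minimum of 2 per month. This is a one-line change with no added patients, visits or data. Its price is that the written bar drops from 2 to about 1.7 per month, and the amendment should say so openly.

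If 2 per month is really intended, write *30 participants recruited within 15 months*. Section 7.1 then has to change to 15 months, and the total duration to 15 + 3 = 18 months if the current 21 is indeed 18 + 3. Section 7.3 stands under either option. Keeping both 2 per month and 18 months would instead require 36 participants, six more than Section 7.3 supports.

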and subacute stroke patients (n=28, days post-stroke: median = 9; range = 5-11), although the authors did not specify the proportion of participants that were in the acute (1-7 days post-stroke) or early subacute phase of stroke (7-30 days post-stroke). One of the exercise test termination criteria was reaching 85% of age-predicted maximum heart rate (HRmax), which is classed as vigorous exercise intensity (45). Over half of the participants exceeded this upper heart rate threshold and no SAEs or AEs were observed. Lastly, in our preliminary work (ESCAPE trial; STH20750), 4 acute stroke patients successfully completed a single 30-minute moderate-intensity exercise session (13/20 RPE) and there were no AEs or SAEs. Importantly, none of the aforementioned studies reported follow-up safety outcomes. **We can confirm that there have been no SAEs or AEs related to aerobic exercise in the 3 months following our investigation.** In summary, there have been approximately 276 reported bouts of aerobic exercise conducted in the acute phase of stroke, ranging from 6 to 30 minutes in duration and from moderate to vigorous intensity. No SAEs have been reported, whereas the AE rate ranged from 0-14.7% (mean 12%). The higher frequency of AEs appears to be related to high exercise volume and the mode of exercise training (e.g. treadmill exercise twice per day for 5 days).

In our proposed aerobic exercise training intervention, participants will exercise at a moderate intensity (40-59% HRR; 12-13/20 RPE). Moderate-intensity aerobic exercise elicits a transient increase in cerebral perfusion and neurotrophin concentration (39,59) which may contribute to improved recovery after stroke (24–26). Exercise duration will gradually increase from 10 minutes in the first session (day 1) to 30 minutes in the fifth session (day 5) (5-minute increment per day). Heart rate (HR) will be monitored continuously during exercise to ensure that moderate intensity is not exceeded. Heart rate reserve – the difference between resting HR and HRmax – represents the capacity for the HR to increase under stress. Measurement of HRmax is not appropriate due to the required vigorous exercise intensity. Instead, age-predicted HRmax will be calculated using the Inbar equation which estimates HRmax with greater accuracy than the commonly used formula of 220-age (66).

Inbar equation: $205.8 - (0.685 \times \text{age})$.

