12.4. Operational definitions for (S)AEs

Adverse events

Any untoward medical or psychological occurrence in a patient or trial subject involved in a trial intervention and which does not necessarily have a causal relationship with this intervention. An adverse event can therefore be any unfavourable and unintended sign, symptom, or disease (including abnormal lab results or a traffic accident) in any subject in a trial (including those in an untreated control group), whether or not considered related to the investigational intervention.

Serious adverse events

Unless exempted by the approved protocol, any untoward medical or psychological occurrence that:

- results in death
- is life-threatening*
- requires inpatient hospitalization or prolongation of existing hospitalization
- results in persistent or significant disability/incapacity
- requires intervention to prevent one of the above occurrences

*Life-threatening in the definition of a SAE refers to an event in which the subject was at risk of death at the time of the event. It does not refer to an event which hypothetically might have caused death if it were more severe.

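### The only safety criterion for progression is one count of related adverse events with no line for seriousness, so one to four related SAEs can read Green while eleven minor related events read Red

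*Protocol*

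**What the plan says.** Section 6.3 introduces the criteria with "Progression to a definitive trial will be considered if the following a priori success criteria are met". Its safety item is a three-band light on one quantity, the number of adverse events related to the intervention. The bottom band is "Green: <5 adverse events related to the intervention", with the action to proceed. The middle band, 5 to 10, calls for review and revision of the protocol. The top band is "Red: >10 adverse events related to the intervention", with the action not to proceed. Section 6.3 has no other safety criterion.

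Elsewhere the protocol separates serious from other events:

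- Objective 1b in section 5 is to "Assess the safety of the intervention via SAEs and AEs".
- Section 8.3 reports the absence of SAEs in earlier work apart from the adverse event rate.
- Section 12.4 defines the two classes separately. An adverse event is "Any untoward medical or psychological occurrence in a patient or trial subject involved in a trial intervention", whether or not it is caused by the intervention. An SAE is such an occurrence that meets one of several criteria, the first of which is that it "results in death".
- Table 6 in section 11 gives the safety outcome as "Number of SAE and AEs related to the intervention", in one row and without a threshold.
- Sections 12.5 and 12.6 set out how SAEs are recorded, reported to the Sponsor and reviewed.

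**The concern.** The light ranks outcomes by how many related events occurred and not by how grave they were. A small number of related serious events falls in the band marked proceed, while a larger number of trivial ones falls in the band marked do not proceed. The purpose of fixing criteria in advance is to settle how the data will be read before they are seen. Here the rule as written gives the wrong reading in the cases where a safety criterion matters most.

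The protocol has reason to provide for such cases. Section 8.4.1 puts the intervention in risk category B, above the risk of standard care, because long-term follow-up data are lacking.

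**Working it through.** **The plan's own figures.** The target sample size reproduces: 24 / (1 − 0.20) = 30. The treadmill study's adverse event rate reproduces: 33 / 224 = 14.73%. The mean rate in section 8.3 reproduces: 33 / 276 = 11.96%, stated as 12%. The cut-offs in 6.3 are given without a derivation, so there is nothing behind them to reproduce.

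**Applying the rule as written.** Under section 12.4 every SAE is also an adverse event, so the first reading below follows from the definitions. The second is shown in case 6.3 meant non-serious events only.

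| Related SAEs | Minor related events | SAEs counted | SAEs not counted |
|---|---|---|---|
| 1 | 0 | Green | Green |
| 4 | 0 | Green | Green |
| 5 | 0 | Amber | Green |
| 0 | 10 | Amber | Amber |
| 0 | 11 | Red | Red |

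On the first reading, one to four related SAEs are Green only while all related events together stay below five. On the second, related SAEs never affect the band.

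**Size of the Green case.** The target of 30 (section 7.3) with equal allocation gives 15 exercised participants. Equal allocation is an assumption, inferred from the minimum of 12 per arm. Related SAEs in four different participants give 4/15 = 26.7%. The exact (Clopper-Pearson) limits are:

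- lower: 0.025 quantile of Beta(4, 12) = 7.8%
- upper: 0.975 quantile of Beta(5, 11) = 55.1%

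With 12 exercised participants, 4/12 = 33% (10% to 65%). Both are Green if there is no further related event.

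**Size of the Red case.** Planned sessions are 15 × 5 = 75 (five per participant, section 12.3.3). Take p = 33/224 from section 4.3, a rate observed without SAEs that the study's authors judged acceptable. Assume independent sessions with at most one event each. The expected count is 75 × 0.1473 = 11.05, and with X ~ Binomial(75, 0.1473):

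- P(Green) = P(X ≤ 4) = 0.01
- P(Amber) = P(5 ≤ X ≤ 10) = 0.43
- P(Red) = P(X ≥ 11) = 0.56

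The Red probability depends on the inputs: it is 0.26 with 60 sessions (12 × 5) at 14.7%, and 0.28 with 75 sessions at the 12% mean rate.

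**How the two cases relate.** They rest on opposite assumptions about minor events. Four SAEs are Green only if nothing else related occurs, whereas at 14.7% per session Green is reached with probability only 0.01. They show what the rule does at its two ends and do not describe one expected trial.

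**The case against.** The strongest reply is that Green does not cause a definitive trial to go ahead. Section 6.3 says progression will be considered if all the criteria are met, so Green on safety is one condition among several. SAE handling is also more than nominal. Under section 12.5 every SAE goes to the Sponsor within 24 hours with its seriousness, causality and whether it was anticipated. Under section 12.6 the Study Doctor keeps benefit and risk under review and examines specific SAEs, and the Principal Investigator passes safety information to the Sponsor. Related serious events would have been seen by these people before any end-of-trial light was read.

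Much of this stands. A reader might infer that the plan sends a trial with related deaths straight to progression, or that nobody would look at them. The documents support neither inference. What the reply does not do is fill the gap: no passage says that a related SAE overrides or qualifies the light, and the Green line itself names the action as proceed.

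A second reply is that the illustration is extreme, since section 8.3 reports no SAEs in about 276 bouts. That is fair as to likelihood. It does not answer a point about what the rule says when such an event does occur.

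A reader might also set four SAEs over 75 sessions against the risk of under 1% in section 8.5.2. That comparison does not hold. The figure there covers complications of any gravity and is not an SAE rate, and SAEs are recorded for 3 months after the intervention, so sessions are not their natural denominator.

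**Conclusion.** The point holds on the text. The one pre-set safety criterion for progression ignores seriousness, and no other section gives a progression line for SAEs. Related SAEs in up to four of 15 exercised participants (27%, exact 95% CI 8% to 55%) satisfy Green if no other related event occurs. A rate of events without any SAE, which the cited authors accepted, would be Red with probability 0.56 over 75 sessions. These figures assume equal allocation, full delivery of sessions and, for the second, independent sessions. The treadmill rate is a yardstick and not a forecast, because section 8.3 itself links it to exercise volume and mode.

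The consequence is softened by the word considered in 6.3 and by the SAE review in 12.5 and 12.6. The gap should still be fixed: it lies in a stated decision rule and costs little to close. The numerical cut-offs are not shown to be wrong.

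**What to change.** Add one line to section 6.3 that takes related SAEs separately from the adverse event count, so that Green is not met on the count alone when a related SAE has occurred and the case goes to review. The trial team sets the SAE threshold and what follows from it. In Table 6, report related SAEs and related adverse events as two counts. Leave the bands at <5, 5 to 10 and >10.

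This needs no new data, since causality and seriousness are already collected for every SAE. The price is that Green becomes harder to reach. If the line were set at one related SAE, the chance that it fires among 15 exercised participants is 1 − (1 − p)^15, with p an assumed risk per participant:

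- p = 1%: 1 − 0.99^15 = 0.14
- p = 2%: 1 − 0.98^15 = 0.26
- p = 5%: 1 − 0.95^15 = 0.54

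The line would also rest on the Investigator's opinion of causality (12.5) in a trial whose on-site staff know the allocation (7.9). The team should weigh this when it chooses the threshold.
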